2.8.5 Cardiac Imaging (MUGA/ECHO)

For cardiac imaging descriptive statistics at baseline and at each post -baseline time(if available) will be summarized and listed.

2.9 Pharmacokinetic endpoints

Not Applicable

2.10 PD and PK/PD analyses

Not Applicable

2.11 Patient-reported outcomes

Not Applicable

2.12 Biomarkers

Not Applicable

2.13 Other Exploratory analyses

Not Applicable

2.14 Interim analysis

Scheduled interim data reviews will occur for the primary endpoint of clinical benefit rate only as required by the Bayesian Hierarchical design. The first interim data review will be performed after the 5 subjects have CBR data available within a cohort. Interim analyses will continue every 3 months thereafter provided at least 10 subjects contribute new CBR data to the subsequent interim. At each interim analysis, the tumor cohorts will be evaluated for early futility and early success by comparing posterior quantities for the response rate to pre-specified early stopping criteria.

There is no plan for a formal interim analysis of safety or other secondary endpoints for this study. However, for publication or other purposes, interim data review of clean data will be performed as necessary. At these interim reviews, patient demographics/baseline characteristics, the primary and secondary endpoints as applicable, and all important safety endpoints will be summarized. No formal report will be issued for these data reviews.

3 Sample size calculation

The sample size was chosen by the usual criteria of obtaining adequate power for the alternative hypothesis of interest as given in Sections 6.2.2 and 6.2.3 of Appendix 4 of protocol. This hypothesis corresponds to a generally effective treatment across cohorts and incorporates variation in treatment effects to reflect the realistic expectation that treatment effects may differ by cohort. In this setting, analytical power calculations are not possible, but the design was simulated to obtain the power of the study as shown in the appendix. The sample sizes shown (minimum of 5 for futility stopping, minimum of 10 for early success and maximum of 24 as a cohort cap) achieve adequate power for the alternative hypothesis. The simulations included the expected variable accrual by simulating a Poisson process with expected accrual also shown in the appendix.

4 Change to protocol specified analyses

As per study team suggestion, the definitions of full analysis set (FAS) and safety set have been changed(defined in [section 2.2](#)).

5 Appendix

5.1 Imputation rules

5.1.1 Study drug

The following rule should be used for the imputation of the dose end date for a given study treatment component:

Scenario 1: If the dose end date is completely missing and there is no EOT page and no death date, the patient is considered as on-going: The patient should be treated as on-going and the cut-off date should be used as the dose end date.

Scenario 1 should not be applicable for final CSR. All patients should have EOT page complete before the Database lock for Final CSR.

Scenario 2: If the dose end date is completely or partially missing and the EOT page is available:

Case 1: The dose end date is completely missing, and the EOT completion date is complete, then this latter date should be used.

Case 2: Only Year(yyyy) of the dose end date is available and yyyy < the year of EOT date:

Use Dec31yyyy

Case 3: Only Year(yyyy) of the dose end date is available and yyyy = the year of EOT date:

Use EOT date

Case 4: Both Year(yyyy) and Month (mm) are available for dose end date, and yyyy = the year of EOT date and mm < the month of EOT date:

Use last day of the Month (mm)

All other cases should be considered as a data issue and the statistician should contact the data manager of the study.

After imputation, compare the imputed date with start date of treatment, if the imputed date is < start date of treatment:

Use the treatment start date

Patients with missing start dates are to be considered missing for all study treatment component related calculations and no imputation will be made. If start date is missing then end-date should not be imputed.

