6.6 Study drug preparation and dispensation

Both PDR001 and LAG525 will be administered intravenously as a 30 minute infusion (up to 2 hour, if clinically indicated). Further instructions for the preparation and dispensation of LAG525 and PDR001 are described in the Pharmacy Manual(s). All dosages prescribed to the patient and all dose changes during the study must be recorded on the Dosage Administration Record CRF.

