7.1.5 Discontinuation of study treatment

Patients may voluntarily discontinue from the investigational treatment for any reason at any time. If a patient decides to discontinue, the investigator should make a reasonable effort (e.g. telephone, e-mail, letter) to understand the primary reason for this decision and record this information in the patient's chart and on the appropriate CRF pages. They may be considered withdrawn if they state an intention to withdraw, fail to return for visits, or become lost to follow-up for any other reason.

The investigator should discontinue investigational treatment for a given patient if he/she believes that continuation would be detrimental to the patient's well-being.

Study treatment may be discontinued if any of the following occur:

- Adverse event
- Lost to follow-up
- Physician's decision
- Progressive disease per defined response criteria
- Study terminated by the sponsor
- Subject/guardian decision
- Protocol deviations that result in significant risk to the patients' safety
- Technical problems

Patients will be withdrawn if any of the following occur:

- Pregnancy
- Death

At the time patients discontinue study treatment, a visit should be scheduled as soon as possible, and within 14 days of the last dose of study drug or within 14 days of the decision to permanently discontinue study treatment, at which time all of the assessments listed for the EOT visit will be performed ([Table 7-1](#)). If the decision to withdraw the patient occurs at a regularly scheduled visit, that visit may become the EOT visit rather than having the patient return for an additional visit. An End of Treatment Phase Disposition CRF page should be completed, giving the date and reason for stopping the study treatment. End of treatment/Premature withdrawal visit is not considered as the end of the study.

At a minimum, all patients who discontinue study treatment, including those who refuse to return for a final visit, will be contacted for safety evaluations during the 150 days following the last dose of study treatment.

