2.1.1.8 On-treatment assessment/event and observation periods

The overall observation period will be divided into three mutually exclusive segments:

1. *Pre-treatment period:* from day of patient's informed consent to the day before first administration of study drug
2. *On-treatment period:* from day of first administration of study drug to 30 days after last administration of study drug (Note: for ongoing patients, from day of first administration of study drug to the analysis cut-off date)
3. *Extended safety follow-up period:* from day 31 to at least day 150 after last administration of study drug or lost to follow-up.

In particular, summary tables for adverse events (AEs) will summarize only on-treatment events, with a start date during the on-treatment period, the so-called treatment-emergent AEs.

All safety data (including those from the pre-treatment and extended safety follow-up period) will be listed and those collected during the pre-treatment and extended safety follow-up period are to be flagged.

Additional summaries will be displayed to report deaths, all AEs, AEs related to study treatment, all SAEs and SAEs related to study treatment collected up to 150 days after last administration of study drug.

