2.4.1 Study treatment

The duration of exposure (weeks), cumulative dose, actual dose intensity and relative dose intensity will be listed and summarized for the study drugs PDR001 and LAG525 based on safety set by means of descriptive statistics. Categories for relative dose intensity of PDR001 and LAG525 will be specified as $\leq 75\%$, $>75\% - \leq 90\%$, $> 90\% - \leq 110\%$ and $> 110\%$; the number and proportion of patients within each category will be presented.

In addition, dose interruptions and dose permanently discontinued (including the reasons for these) will be listed and summarized. All dosage administration records will be listed.

Duration of exposure to study treatment

Duration of exposure to study treatment is calculated as follows:

Duration of exposure to study drug (days) = (last date of exposure to study drug) – (date of first administration of study drug) + 1.

Duration of exposure (weeks) = (Duration of exposure, days) / 7.

The last date of exposure to PDR001 Q3W is the planned end date of the last cycle in which the last non-zero dose of PDR001 was last administered (i.e last date of administration + 20 day)).

Similarly, the last date of exposure to LAG525 Q3W is defined as the last date of LAG525 administration + 20 days.

The last date of exposure for the combination PDR001+LAG525 is the last date of exposure to PDR001 or LAG525 (defined as above), whichever is later.

Note: If the patient died or was lost to follow-up before the derived last date, the last date of exposure to investigational drug/study treatment is the date of death or the date of last contact, respectively.

Summary of duration of exposure of study drug in appropriate time units will include categorical summaries (<6, 6-<12, 12-<18, 18-<24 and ≥ 24 weeks) and continuous summaries (i.e. mean, standard deviation etc) in weeks. The duration of exposure to study drug may include periods of temporary interruption (zerodose periods).

Actual cumulative dose

Actual cumulative dose is defined as the total dose administered over the duration for which the subject is on the study treatment as documented in the Dose Administration eCRF, and will be summarized for each of the study treatment components separately.

For patients who did not take any drug the cumulative dose is by definition equal to zero.

- Actual dose (mg) = Sum of (actual dose per an infusion) for all infusions.

Dose intensity and relative dose intensity

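### SAP 5.1.1 fills a missing dose end date with the end-of-treatment date, year end or month end, although each dose is a same-day infusion; if used as the last administration date, it would lengthen exposure and safety windows

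*SAP*

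**What the plan says.** SAP 5.1.1 imputes the dose end date for each study treatment component. Scenario 2 applies when the EOT page is available:

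- Case 1, date fully missing: "The dose end date is completely missing, and the EOT completion date is complete, then this latter date should be used".
- Case 2, only the year known and earlier than the EOT year: "Use Dec31yyyy".
- Case 3, only the year known and equal to the EOT year: the EOT date.
- Case 4, year and month known, same year as EOT and an earlier month: the last day of that month.

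Any other pattern goes to the data manager. The only check on the result is against the start of treatment: "compare the imputed date with start date of treatment, if the imputed date is < start date of treatment", the treatment start date is used. If the start date is missing, the end date is not imputed.

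Protocol 6.6 describes the dosing: "Both PDR001 and LAG525 will be administered intravenously as a 30 minute infusion", extendable to 2 hours. Protocol 7.1.5 places the EOT visit "within 14 days of the last dose of study drug or within 14 days of the decision to permanently discontinue study treatment".

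SAP 2.1.1.3 and 2.1.1.5 define last administration as the last date on which a non-zero dose was given and recorded on the dose administration record (DAR). SAP 2.4.1 takes the last date of exposure as "last date of administration + 20 day"s. SAP 2.1.1.8 runs the on-treatment period "from day of first administration of study drug to 30 days after last administration of study drug".

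**The concern.** The rules in SAP 5.1.1 suit a drug taken daily until treatment stops, where the last dose may well fall near the EOT date. They do not suit an infusion given once every 21 days. The true end date of an infusion record is its own start date, and the rule runs only when a start date exists. It therefore passes over a known date in favour of a later one.

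If the imputed date were carried forward as last administration, it would move the end of exposure, the denominator of dose intensity in mg per unit time, the 30-day on-treatment window behind the main adverse event (AE) tables, and the 150-day limit. SAP 2.4.1 would then add a 20-day dosing interval to a date that may already lie beyond that interval. Nothing compares the imputed date with the infusion's own start date.

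**Working it through.** **Inputs.** Cycle length is 21 days (Protocol 7.1.4), so with no delays infusion n falls on Day 1 + 21(n − 1). Exposure in days = (last administration + 20) − first administration + 1 (SAP 2.4.1). On-treatment end = last administration + 30 (SAP 2.1.1.8).

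**Check of the formula.** One infusion on Day 1 gives (1 + 20) − 1 + 1 = 21 days, which is one cycle, as intended.

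**Direction.** Let g be the imputed date minus the true infusion date. EOT does not precede the last infusion, and a month end or year end cannot precede a date within that month or year. So g ≥ 0 in all four cases.

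**Size of g for a final infusion.**

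- EOT within 14 days of the last dose: 0 to 14 days.
- Decision to stop at the next due visit: 21 days if that visit serves as EOT, which Protocol 7.1.5 allows, or 21 + 14 = 35 days if EOT takes the full further fortnight.
- Extreme: a 12-week interruption (Protocol 6.3.1), counted here from the last infusion, then 14 days to EOT: 84 + 14 = 98 days.
- Month end: 0 to 30 days (the maximum is an infusion on the 1st of a 31-day month).
- Year end: 0 to 97 days if EOT is within 98 days of the infusion, because EOT must then fall in the next year. Without that bound the arithmetic limit is 364 days.

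**Effect, if the imputed date is used as last administration.** Exposure E becomes E + g, the window end moves by g, and dose intensity is multiplied by E/(E + g).

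| Infusions | g (days) | Exposure, true | Exposure, imputed | SAP category (weeks) | On-treatment end | Dose intensity ratio |
|---|---|---|---|---|---|---|
| 1 | 14 | 21 d (3.0 wk) | 35 d (5.0 wk), +67% | <6, unchanged | Day 31 → 45 | 21/35 = 0.60 |
| 1 | 98 | 21 d (3.0 wk) | 119 d (17.0 wk), +467% | <6 → 12-<18 | Day 31 → 129 | 21/119 = 0.18 |
| 4 | 14 | 84 d (12.0 wk) | 98 d (14.0 wk), +17% | 12-<18, unchanged | Day 94 → 108 | 84/98 = 0.86 |
| 4 | 98 | 84 d (12.0 wk) | 182 d (26.0 wk), +117% | 12-<18 → ≥24 | Day 94 → 192 | 84/182 = 0.46 |
| 8 | 14 | 168 d (24.0 wk) | 182 d (26.0 wk), +8% | ≥24, unchanged | Day 178 → 192 | 168/182 = 0.92 |
| 8 | 98 | 168 d (24.0 wk) | 266 d (38.0 wk), +58% | ≥24, unchanged | Day 178 → 276 | 168/266 = 0.63 |

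A one-infusion patient first changes exposure category at g = 21, where exposure is 42 days (6.0 weeks).

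**What does not move.** Under SAP 2.4.1, relative dose intensity = (actual dose / duration) / (planned dose / duration) = actual / planned, so duration cancels. Cumulative dose is a sum over infusions and does not use end dates. The clinical benefit rate does not use the dose end date.

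**If SAP 2.1.1.3 and 2.1.1.5 are followed literally**, last administration is the recorded infusion date, g = 0, and every row returns to its true value.

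**The case against.** The strongest reply is that the SAP never says the imputed date is used for anything that matters. Exposure and the AE windows hang on last administration, and an imputed EOT date is neither administered nor recorded on the DAR. A reader might infer that exposure and the on-treatment AE tables are overstated in this trial. The documents do not support that. It would need a missing end date on a record that sets the last date, and programming that departs from SAP 2.1.1.3. This part of the objection stands.

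It does not clear the rule. SAP 5.1.1 excludes patients with missing start dates from treatment-related calculations, which suggests that its dates are meant to enter them. If the imputed date feeds nothing, the rule has no purpose. Either way the sections need to be reconciled.

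Other points against, all of which stand:

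- Missing end dates should be few. Site staff give every infusion and record it at each visit (Protocol 6.6.3.1), and missing values are queried (Protocol 9.4).
- The 98-day figure combines a full 12-week interruption with the longest EOT delay. It is not typical.
- The SAP does not define the EOT completion date. Protocol 7.1.5 says the EOT disposition page carries the date of stopping treatment, which could be earlier than the visit. Protocol Appendix 1 (14.1.30) puts the EOT visit within 7 days of last treatment, which differs from 7.1.5.
- AEs and serious AEs through 150 days are summarised separately (SAP 2.8.1), so a reclassified event within that period would still appear there.
- Exposure is capped at death or last contact for patients who died or were lost to follow-up (SAP 2.4.1).
- Scenario 1, which uses the cut-off date, is stated not to apply to the final study report, so changing it would achieve little.

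**Conclusion.** The rule is wrong for these drugs as written: it replaces a known date with one that can only be the same or later. Whether it distorts any result is not established. The effect is conditional on the imputed date being used as last administration, on which the SAP is silent.

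Given that use, the shift per affected patient is 0 to 14 days when EOT is within 14 days of the last dose, 0 to 30 days for month end, and about 98 days in the extreme case. The 98 days assumes that the EOT date is the visit date and that the 12 weeks run from the last infusion. It is an illustration and not a strict ceiling, since Protocol 6.3.1 speaks of more than 12 weeks and allows exceptions.

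Exposure duration, dose intensity per unit time and the 30-day and 150-day windows would be affected for that patient. Relative dose intensity, cumulative dose and the primary analysis would not. The number of affected records is not given and is probably small. This is a correction to a stated rule, not a demonstrated bias.

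**What to change.** Replace Scenario 2 of SAP 5.1.1 for PDR001 and LAG525 with:

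> If the end date of an infusion record is missing or partial, set it to the start date of that same infusion record.

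This removes the EOT, 31 December and month-end defaults for these drugs. Keep the rule that no end date is imputed when the start date is missing. State in SAP 2.1.1.3, 2.1.1.5 and 2.4.1 that the last administration date is the recorded infusion date on the DAR.

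The cost is a few sentences and a small program change, with no statistical downside and no change to dosing or clinical management. The SAP history already lists post-lock changes, so there is a route for this one. If no dose end date was imputed, one sentence in the study report saying so closes the point.

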5.1.2 AE and ConMeds date imputation

Table 5-1 Imputation of start dates (AE, CM)

Missing Element	Rule
day, month, and year	
• No imputation will be done for completely missing dates
day, month	
• If available year = year of study treatment start date then

	
 ○ If stop date contains a full date and stop date is earlier than study treatment start date then set start date = 01JanYYYY ○ Else set start date = study treatment start date ● If available year > year of study treatment start date then 01JanYYYY ● If available year < year of study treatment start date then 01JulYYYY
day	
 ● If available month and year = month and year of study treatment start date then 
 ○ If stop date contains a full date and stop date is earlier than study treatment start date then set start date= 01MONYYYY. ○ Else set start date = study treatment start date. ● If available month and year > month and year of study treatment start date then 01MONYYYY ● If available month and year < month year of study treatment start date then 15MONYYYY

Table 5-2 Imputation of end dates (AE, CM)

Missing Element	Rule
	(*=last treatment date plus 150 days not > (death date, cut-off date, withdrawal of consent date))
day, month, and year	
 ● Completely missing end dates (incl. ongoing events) will be imputed by the end date of the on-treatment period*
day, month	
 ● If partial end date contains year only, set end date = earliest of 31DecYYYY or end date of the on-treatment period *
day	
 ● If partial end date contains month and year, set end date = earliest of last day of the month or end date of the on-treatment period*

Any AEs and ConMeds with partial/missing dates will be displayed as such in the data listings.
Any AEs and ConMeds which are continuing as per data cut-off will be shown as 'ongoing' rather than the end date provided.

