 - Other east Asian
 - Southeast Asian
 - West Asian
 - Mixed ethnicity
 - Other
 - missing
- Child bearing potential for female patients
 - Able to bear children
 - Premenarche
 - Post menopausal
 - Sterile-of child bearing age

Baseline characteristic variables include:

- Eastern Cooperative Oncology Group - Performance Status (ECOG PS)
 - 0 - Fully active, able to carry on all pre-disease performance without restriction
 - 1 - Restricted in physically strenuous activity but ambulatory and able to carry out work of a light or sedentary nature, e.g., light house work, office work
 - 2 - Ambulatory and capable of all self-care but unable to carry out any work activities. Up and about more than 50% of waking hours

- 3 - Capable of only limited self-care, confined to bed or chair more than 50% of waking hours
- 4 - Completely disabled. Cannot carry on any self-care. Totally confined to bed or chair
- Missing
- Body weight (kg)
- Body height (cm)
- Body surface area (BSA) (m²)
BSA to be calculated as per the DuBois and DuBois formula:
 $= 0.20247 \times \text{height}(\text{m})^{0.725} \times \text{weight}(\text{kg})^{0.425}$
- Cardiac imaging (Left Ventricular Ejection Fraction [LVEF])
- Body mass index(BMI)(kg/m²)
BMI to be calculated as (weight[kg] / (height[m]²) using weight at baseline.

Diagnosis and extent of cancer

Summary statistics will be tabulated for diagnosis and extent of cancer. This analysis will include the following: diagnosis of disease, details of tumor histology/cytology (based on predominant histology/cytology), histological grade, stage at initial diagnosis, time since initial diagnosis to first administration of study drug (in months), time since most recent relapse/progression to first administration of study drug (in months), stage at time of study entry, types of lesions at baseline, and number and type of metastatic sites involved.

Note: Types of lesions at baseline (presence/absence of target and non-target lesions and index and non-index lesions) will be based on the data collected on the [RECIST 1.1 Target Lesion Assessments], [RECIST 1.1 Non-Target Lesion Assessments],[Cheson tumor evaluation - Index lesion] and Cheson tumor evaluation – Non-Index lesion] eCRF pages. Metastatic sites will be based on the [Diagnosis and Extent of Cancer] eCRF page.

Medical history

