2.4.2 Prior concomitant and post therapies

Prior anti-neoplastic therapies

The number and percentage of patients who received any prior anti-neoplastic medications, prior anti-neoplastic radiotherapy or prior anti-neoplastic surgery will be summarized overall.

This summary will include medication: type of last therapy, setting at last therapy and best response to last medication. A separate listings will be produced for prior anti-neoplastic medications, radiotherapy, and surgery.

The above analyses will be performed using the FAS. Anti-neoplastic medications will be coded using the WHO Drug Dictionary (WHO-DD); anti-neoplastic surgery will be coded using MedDRA.

Post treatment anti-neoplastic therapy

Anti-neoplastic therapies since discontinuation of study treatment will be listed for the FAS in three separate listings: medications, radiotherapy, and surgery.

Concomitant therapy

Concomitant therapy is defined as all interventions (therapeutic treatments and procedures) other than the study treatment administered to a patient coinciding with the study treatment period. Concomitant therapy include medications (other than study drugs) starting on or after the start date of study treatment or medications starting prior to the start date of study treatment and continuing after the start date of study treatment.

Concomitant medications will be coded using the World Health Organization (WHO) Drug Reference Listing (DRL) dictionary that employs the WHO Anatomical Therapeutic Chemical (ATC) classification system and summarized by lowest ATC class and preferred term using frequency counts and percentages. Surgical and medical procedures will be coded using MedDRA and summarized by SOC and preferred term. Concomitant medications with immunosuppressive intent will be summarized by lowest ATC class and preferred term using frequency counts and percentages. Concomitant medications with immunosuppressive intent will be summarized by lowest ATC class and preferred term using frequency counts and percentages. These summaries will include:

1. Medications starting on or after the start of study treatment but no later than 30 days after start of last dose of study treatment and
2. Medications starting prior to start of study treatment and continuing after the start of study treatment.

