5.1.2.3 Other imputations

Incomplete date of initial diagnosis of cancer and date of most recent recurrence

Missing day is defaulted to the 15th of the month and missing month and day is defaulted to 01-Jan.

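### SAP date-imputation rules can start a medication after its own stop date and count it as on treatment, and can make time since relapse negative

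*SAP*

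**What the plan says.** SAP 5.1.2, Table 5-1, imputes incomplete start dates for adverse events and concomitant medications. For a year-only start in the year of first dose there are two branches. The first is "If stop date contains a full date and stop date is earlier than study treatment start date then set start date = 01JanYYYY". Everything else goes to "Else set start date = study treatment start date". For earlier periods the rules are "If available year < year of study treatment start date then 01JulYYYY" and "If available month and year < month year of study treatment start date then 15MONYYYY"; neither looks at the stop date.

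Table 5-2 handles incomplete stops: "If partial end date contains month and year, set end date = earliest of last day of the month" or the end of the period.

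The tables select on the start date. SAP 2.4.2 includes "Medications starting on or after the start of study treatment but no later than 30 days after start of last dose" of study treatment, and SAP 2.1.1.8 counts adverse events whose start lies in the on-treatment period.

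For the date of initial diagnosis and of the most recent recurrence, SAP 5.1.2.3 states: "Missing day is defaulted to the 15th of the month and missing month and day is defaulted to 01-Jan". The recurrence date feeds the months from last relapse or progression to first dose, a baseline item in SAP 2.3.1.

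SAP 5.1.1 has an order check for imputed dose end dates. SAP 5.1.2 and 5.1.2.3 have none.

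**The concern.** Imputing toward treatment start is a reasonable convention when the record leaves the timing open. Here it does not. A stop month before the month of first dose already shows that the record ended before treatment, and the rule discards that information only because the day is missing. The first branch shows that the SAP means such records to be pre-treatment, so the partial stop looks like an oversight.

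The result is a medication that starts after it stops and is tabulated as started on study. The table of medications with immunosuppressive intent is included. Protocol 6.4.3 restricts systemic steroids and other immunosuppressants on study, so a pre-study course could be read as on-study use.

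The relapse rule has a similar gap. In a population that must have relapsed or refractory disease at entry, a negative time since relapse cannot be right, and it would enter the summary statistics.

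**Working it through.** The plan states no figure on this point, so there is none to reproduce. The rules are applied literally.

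**A. Start set to first dose although the stop is earlier**

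Inputs: start 2018, stop APR2018, first dose 10 Jul 2018 (illustrative dates).

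1. The start year equals the first-dose year and the stop is not a full date, so the second branch applies: start = 10 Jul 2018.
2. Table 5-2: stop = last day of the month = 30 Apr 2018.
3. Start minus stop = 31 (May) + 30 (June) + 10 (July) = 71 days.
4. The start equals the first-dose date, so the record counts as starting on treatment.

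With a full stop date of 10 Apr 2018 instead, the start becomes 01 Jan 2018. The order is then correct and the record is pre-treatment. The quoted branch therefore works; the fault is its full-date condition together with the branch that follows.

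This is deterministic. If the stop month is any month before the first-dose month in that year, the imputed stop is earlier than first dose and the imputed start equals first dose. If the stop month is the first-dose month, the imputed stop is the month end, there is no inversion, and the timing is truly open.

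**B. The other two branches**, first dose 15 Jun 2018

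- Start 2017, stop 10 Mar 2017: start = 01 Jul 2017, which is 21 + 30 + 31 + 30 + 1 = 113 days after the stop.
- Start MAY2018, stop 05 May 2018: start = 15 May 2018, 10 days after the stop.

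Both are inverted, but both stay before first dose and outside the on-treatment tables.

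**C. Missing relapse day**

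Relapse JUN2018, first dose 05 Jun 2018: relapse = 15 Jun 2018, interval = 5 − 15 = −10 days, or −10/30.3475 = −0.33 months (month length from SAP 2.1.1.9). In general, a first dose on day d < 15 of the relapse month gives d − 15 days, that is −14 to −1.

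Share of same-month cases affected, assuming a 30-day month, uniform dates and relapse strictly before dosing:

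- All ordered pairs: 1 + 2 + … + 29 = 435.
- Pairs with first dose on days 2 to 14: 1 + 2 + … + 13 = 91.
- Share: 91/435 = 20.9%.

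**D. Year-only relapse set to 01 Jan**

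The imputed date is too early by 0 to 364 days in a 365-day year. If the true date is uniform over the year, the mean is 182 days, or 182/30.3475 = 6.0 months. If the relapse year is the dosing year the error is bounded by first dose: for first dose 15 Jun it is at most 165 days (5.4 months) and 2.7 months on average under uniformity. The error has one direction and does not put relapse after first dose. It can put relapse before a recorded diagnosis in the same year: diagnosis 20 Mar 2017 with relapse 2017 gives 31 + 28 + 19 = 78 days before diagnosis.

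**The case against.** **Adverse events.** A reader might infer that the treatment-emergent adverse event tables are contaminated. The documents do not support that. Protocol 8.1.1 counts events only after consent, and protocol 7.1.2 limits screening to 21 days before dosing. A record that stopped 71 days before first dose would not be an adverse event in this trial. An affected event needs a month end inside the screening window and a site that knew the stop month but only the start year. This objection stands, and the exposure is close to nil.

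**Other safeguards.** SAP 2.4.2 defines concomitant therapy as coinciding with the treatment period and flags therapies that start and end before PDR001. Listings show partial dates as recorded, and protocol 9.4 provides for queries. A careful reader of the listings could therefore spot the record. None of this changes the rule that feeds the tables, and a flag that used the imputed start would miss the record. SAP 5.1.2.1 declares prior-therapy imputation not applicable, but protocol 6.4.1 names a single Prior/Concomitant Medications form, so these records do meet Table 5-1.

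**The relapse share.** Days 1 to 14 are 168/365 = 46% of the calendar, and it is tempting to quote that. It treats first dose as independent of relapse, although relapse must come first; the 21% in C respects the order. Exclusion criterion 12, the two-week gap after systemic therapy, lowers it further. A patient treated up to relapse cannot be dosed before day 15 of that month, so the interval cannot be negative.

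**The 01 Jan default.** Six months too early might be read as another impossible order. It is an early default and an average under an assumed distribution. Replacing it with mid-year is a preference and carries its own risk: diagnosis 2017 with relapse MAR2017 is ordered correctly now (01 Jan, then 15 Mar), but a 01 Jul default would put diagnosis after relapse.

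**Conclusion.** The point holds within narrow limits. As written, Table 5-1 puts every record with a year-only start in the first-dose year and a month-and-year stop in an earlier month on treatment, with its start after its stop. SAP 5.1.2.3 allows a negative time since relapse of 1 to 14 days when relapse and first dose share a month and first dose falls before the 15th: about 21% of same-month cases under uniform dates with relapse first, and fewer given the two-week washout. The 01 Jan default is a one-way early bias of 0 to 364 days.

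How often these patterns occur is not given; that partial dates are commonest among prior medications is an assumption. The reach is small: concomitant-medication tables, including immunosuppressive intent, and one baseline descriptor. That descriptor is not among the subgroups in SAP 2.2.3. The clinical benefit rate and the Bayesian decisions do not use these dates.

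**What to change.** - **Table 5-1.** Impute the stop by Table 5-2 first and compare that date with first dose. If it is earlier, set the start to the earliest date its recorded parts allow. In every branch, never let an imputed start exceed the stop.
- **SAP 5.1.2.3.** Cap imputed diagnosis and relapse dates at the day before first dose, and do not let an imputed relapse precede diagnosis. If the cap contradicts the recorded month (first dose on day 1), query the record.
- **Optional.** Use a mid-year default for year-only dates, only with the diagnosis-before-relapse check in place.

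The cost is a few lines of SAP text and code. It is not nil: the SAP history marks the latest changes as made after database lock, so the revised rules would be post hoc, should be documented as such, and require rerunning the affected descriptive tables. A check for starts after stops and negative intervals would first show how many records have impossible orders.
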